## **4.2 Clinical Efficacy**

### **4.2.1 Endpoints & Assessment Methods**

Clinical efficacy will be determined by objective response rate (ORR), disease control rate (DCR), duration of response, progression-free survival (PFS), and overall survival (OS). The primary method of assessment of tumor response will be the Response Evaluation Criteria for Solid Tumors (RECIST) 1.1, and the secondary method of response evaluation will be irRECIST (see Section 8.4)

#### **4.2.1.1 Tumor Response and Overall Response Rate**

##### *4.2.1.1.1 Tumor Response outside the Irradiated Fields*

ORR will be evaluated at Weeks 12 and 18 as a secondary endpoint of this study.

Tumor imaging assessments (e.g., CT, MRI, PET, etc.) of chest, abdomen, pelvis, and CNS for assessment of tumor size and distribution may be employed as deemed appropriate by investigators. Every attempt should be made to use whichever imaging technique(s) test(s) are used initially for repeat evaluations throughout the study. End of study tumor assessment will be 6 weeks from prior assessment, at the Investigator's discretion, and in accordance with the appropriate evaluation method.

Radiographic imaging evaluations are considered standard of care for subjects treated with ipilimumab/nivolumab. Subjects treated off protocol with apparent progressive disease at Weeks 12 or 18 are encouraged to undergo a repeat radiographic assessment of disease approximately 4 to 6 weeks later to confirm progression.

Study radiologists will be informed as to which lesions are intended to undergo RT. The lesions undergoing RT will not be included in the total tumor burden assessment. A separate calculation of response within the irradiated field will be determined as described in Section 4.2.1.1.2.

##### *4.2.1.1.2 Tumor Response within Irradiated Fields*

Since the lesions that undergo RT are not included in the overall tumor burden for purposes of overall response assessments, response within the irradiated field will be separately determined.

The determination of response within the irradiated tumor burden is an independent calculation from the determination of response overall for the tumor burden that does not receive RT.

#### **4.2.1.2 Disease Control Rate**

Disease Control Rate (DCR) will be evaluated at Weeks 12 and 18 as a secondary endpoint of this study. DCR is defined as the percentage of evaluable subjects with SD, PR, or CR.

#### **4.2.1.3 Duration of Response**

Duration of response will be determined for each subject with time origin at the first occurrence of response until the first occurrence of progression or date of death if the subject dies due to

any causes before progression. Every effort will be made to follow subjects for progression after they discontinue the study.

#### **4.2.1.4 Progression-free Survival**

PFS will be defined as the number of days from the date of the first dose of study drug to the date of earliest disease progression based on the appropriate response evaluation method, or to the date of death, if disease progression does not occur. Subjects who do not progress and are still alive will be censored on the date of last follow-up or start of new treatment, whichever comes first. Every effort will be made to follow subjects for progression after they discontinue the study.

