### 3.1.10 Subject Withdrawal from Treatment or from Study

A subject will be **withdrawn from study treatment** for any of the following reasons:

1. Pregnancy or intent to become pregnant.
2. Clinical, symptomatic or radiographic progression warranting alternative treatment.
3. Significant protocol violation or noncompliance that, in the opinion of the Investigator or Sponsor, warrants withdrawal.
4. Initiation of alternative anticancer therapy including another investigational agent.
5. Development of intercurrent, non-cancer related illnesses that prevent either continuation of therapy or regular follow-up.
6. Withdrawal of consent for further treatment.

7. Best medical interest of the subject (at the discretion of the Investigator)
8. Discontinuation criteria per Section 8.3.

Subjects who are withdrawn from study treatment should undergo the planned On Study Follow-up through 100 days after the last study drug administration (see the Study Flowchart in Section 3.2) and enter the Post Study Follow-up phase (see Section 3.1.16).

A subject will be **withdrawn from the study** for the following reasons:

1. Best medical interest of the subject (at the discretion of the Investigator)
2. Withdrawal of consent for all follow-up.
3. Lost to follow-up
4. Death

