### **3.1.16 On Study and Post-Study Follow-up**

All subjects, whether they complete the study as planned, discontinue treatment, or prematurely withdraw from the study as per Section 3.1.10, will be followed as per institutional guidelines in accordance with the usual standard of care principles.

On Study Follow-up will be conducted for 100 days after the last study drug administration according to the flowchart in Section 3.2. Refer to Section 7.1.5 for information on recording AEs during the On Study Follow-up.

In addition to the On Study Follow-up, there will be a Post Study Follow-up, during which clinical outcomes data (dates of progression/relapse and survival) will be collected at least every 12 ( $\pm$  1) weeks for 3 years after completion of 100-day On Study Follow-up. For subjects who do not continue Post Study Follow-up at one of the study sites after the end of study, the Principal Investigators or the clinical team, under the supervision of the Principal Investigator, will obtain the data through review of outside records or communication with the subject or his/her physician.

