### 3.2 Study Flowchart

Study Section	Screening	Treatment								Final Assessment and Ongoing Treatment/ Assessments d	On Study Follow-up a,e	Post-Study Follow-up (Section 3.1.16)
		Week 1 (Cycle 1)	Week 4 (Cycle 2)	Week 7 (Cycle 3)	Week 10 (Cycle 4)	Week 12	Week 14	Week 16	Week 18			
Study Week												
Study Day	-28 to 0 (or as stated)	1	22 (± 3)	43 (± 3)	64 (± 3)	78 (± 3)	92 (± 3)	106 (± 3)	120 (± 3)	2 weeks (± 3 days) after last study drug	30 (±4), 70 (±4) and 100-107 days after last study drug (AEs and pregnancy tests)	(Starts after completion of 100-day On Study Follow-up) Q12W (± 7 d) for 3 years
Drug Administration Cohort A												
Ipilimumab f IV		X	X	X	X							
Nivolumab f IV		X	X	X	X	X	X	X	X	X d		
Radiotherapy b,f (30 Gy over 10 fractions of 3 Gy)		X										
Drug Administration Cohort B												
Ipilimumab f IV		X	X	X	X							
Nivolumab f IV		X	X	X	X	X	X	X	X	X d		
Radiotherapy b,f (27 Gy over 3 fractions of 9 Gy)		X										
Tumor & Disease Assessments												
Disease Staging (date/stage at first diagnosis and study entry)	X											
Disease Assessment by RECIST 1.1 and irRECIST	X					X			X	X d (Week 24, then Q12W ± 7 days)		
Other Procedures & Examinations												
Eligibility Assessment and Informed Consent	X											
Demographics (including DoB, sex, height, race, ethnicity)	X											
Medical History	X											
Physical Exam (including weight)	X	X	X	X	X	X	X	X	X	X d		

CONFIDENTIAL

Study Section	Screening	Treatment								Final Assessment and Ongoing Treatment/ Assessments d	On Study Follow-up a,e	Post-Study Follow-up (Section 3.1.16)
		Week 1 (Cycle 1)	Week 4 (Cycle 2)	Week 7 (Cycle 3)	Week 10 (Cycle 4)	Week 12	Week 14	Week 16	Week 18			
Study Week	Study Day	1	22 (± 3)	43 (± 3)	64 (± 3)	78 (± 3)	92 (± 3)	106 (± 3)	120 (± 3)	2 weeks (± 3 days) after last study drug	30 (±4), 70 (±4) and 100-107 days after last study drug (AEs and pregnancy tests)	(Starts after completion of 100-day On Study Follow-up) Q12W (± 7 d) for 3 years
Electrocardiogram (baseline and as clinically indicated)	X											
Vital Signs (temperature, HR, BP, RR)	X	X	X	X	X	X	X	X	X	X d		
ECOG Performance Status	X	X	X	X	X	X	X	X	X	X d		
Concomitant Medications/Procedures	X	X	X	X	X	X	X	X	X	X d		

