Note: Additional assessments may be evaluated at the Investigator's discretion and per standard of care. Indicated assessments within this chart define clinical data to be captured in the eCRF. Standard of Care procedures may be used for eligibility assessments, provided they meet the criteria specified in either the inclusion criteria or flowchart.

a Subjects will be followed for 100 days after the last dose of study drug as a part of On Study Follow-up; during this time, all AEs will be collected at 30 (±4), 70 (±4) and 100-107 days.

b Radiotherapy will be delivered by standard or high dose palliative RT as per cohort assignment.

c Tumor biopsies are optional but are encouraged. Biopsies are prohibited from compromising the requirement for at least one measurable lesion not undergoing RT.

d **Final Assessment** will be 2 weeks (± 3 days) after last study drug, followed by On Study Follow-up and Post Study Follow-up. A repeat disease assessment scan is not required at the final assessment visit if a scan was done within the previous 6 weeks before the final assessment visit. Subjects who do not continue treatment with nivolumab after Week 18 do not need to have a repeat pregnancy test (if applicable) at the final assessment if the subject had this assessment at Week 18.

**For those subjects who are continuing on nivolumab after Week 18 at 240 mg every 2 weeks ±3 days**, Study Visits will continue every 2 weeks ± 3 days during treatment, followed by the Final Assessment Visit, On Study Follow-up, and Post Study Follow-up after the last nivolumab treatment.

Per Amendment 5, nivolumab monotherapy continuing after Week 18 may be given as 480 mg every 4 weeks ±3 days, starting on Week 20, followed by Weeks 24, 28, etc.

**For those subjects who are continuing on nivolumab after Week 18 at 480 mg every 4 weeks ±3 days**, Study Visits will continue every 4 weeks ± 3 days during treatment, followed by the Final Assessment Visit, On Study Follow-up, and Post Study Follow-up after the last nivolumab treatment.

Subjects continuing nivolumab monotherapy, subjects who complete study treatment as responders, and subjects who have not progressed (either in irradiated or non-irradiated tumor burden) will have an additional scan (disease assessments by RECIST 1.1/ irRECIST) at Week 24 and subsequent scans Q12W (± 7 days) until progression or start of alternate anti-cancer therapy.

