#### **4.2.1.5 Overall Survival**

OS will be measured for each subject from the date of the first dose of study drug until the recorded date of death or last follow-up. Subjects who are still alive will be censored on the date of last follow-up. Every effort will be made to follow subjects for OS after they discontinue the study.

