#### **4.2.2 Subject Evaluation & Statistics**

The Intent-To-Treat (ITT) Population for clinical efficacy is defined as all subjects who receive at least one dose of study drug or RT.

The Per-Protocol (PP) Population for clinical efficacy is defined as all subjects who received at least 75% of the scheduled doses of the study drug and RT over the first 2 cycles, as well as, respective disease assessments, without major protocol violations.

The analysis will be based on both ITT and PP populations.

Tumor Response will be summarized and analyzed descriptively for each cohort and analysis population.

Tumor response rates will be assessed overall and for each cohort and tabulated with the 95% confidence intervals assuming binomial distribution.

For time-to-event analyses, Kaplan-Meier methodology will be implemented to estimate the median duration of response, median PFS, and median OS at Weeks 12 and 18.

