## 1. For Patients with Measurable Disease (i.e., Target Disease)

Target Lesions	Non-Target Lesions	New Lesions	Overall Response	Best Overall Response when Confirmation is Required*
CR	CR	No	CR	≥4 wks. Confirmation**
CR	Non-CR/Non-PD	No	PR	≥4 wks. Confirmation**
CR	Not evaluated	No	PR	
PR	Non-CR/Non-PD/not evaluated	No	PR	
SD	Non-CR/Non-PD/not evaluated	No	SD	documented at least once ≥4 wks. from baseline**
PD	Any	Yes or No	PD	no prior SD, PR or CR
Any	PD***	Yes or No	PD	
Any	Any	Yes	PD	

\* See RECIST 1.1 manuscript for further details on what is evidence of a new lesion.  
 \*\* Only for non-randomized trials with response as primary endpoint.  
 \*\*\* In exceptional circumstances, unequivocal progression in non-target lesions may be accepted as disease progression.  
 Note: Patients with a global deterioration of health status requiring discontinuation of treatment without objective evidence of disease progression at that time should be reported as “*symptomatic deterioration.*” Every effort should be made to document the objective progression even after discontinuation of treatment.

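### PFS censoring is tied to an undefined last follow-up or to new treatment rather than to the last tumour assessment, so unscanned time and symptomatic switchers can make PFS look better

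*Combined protocol and SAP*

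**What the plan says.** Section 4.2.1.4 counts a PFS event on the date of progression by the applicable response method (RECIST 1.1 first, irRECIST second) or at death. For everyone else, "Subjects who do not progress and are still alive will be censored on the date of last follow-up or start of new treatment", whichever is earlier. Section 4.2.1.5 uses the same anchor for OS: "Subjects who are still alive will be censored on the date of last follow-up". Neither section defines it.

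Not every contact includes a scan. The On Study Follow-up column of the flowchart (Section 3.2) runs to "100-107 days after last study drug (AEs and pregnancy tests". In the post-study phase (Section 3.1.16), for subjects not followed at a study site, the team "will obtain the data through review of outside records or communication with the subject or his/her physician".

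Section 3.1.10 lists "Clinical, symptomatic or radiographic progression warranting alternative treatment" as a reason to stop study treatment. The note under the RECIST 1.1 response table in Section 8.4 gives a separate label to "global deterioration of health status requiring discontinuation of treatment without objective evidence of disease progression". Flowchart footnote d schedules a Week 24 scan for subjects who have not progressed and then "subsequent scans Q12W (± 7 days) until progression or start of alternate anti-cancer therapy". For the analysis, Section 4.2.2 says "Kaplan-Meier methodology will be implemented to estimate the median duration of response, median PFS, and median OS at Weeks 12 and 18".

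**The concern.** There are two separate mechanisms.

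**Unscanned time.** Progression is found by assessment, but the censoring date may be set by contact. If last follow-up means last contact, a subject who misses or stops scans is kept at risk, and counted as progression-free, over a period in which progression was not looked for by the criteria that define it.

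**Switching after symptomatic failure.** A subject who is withdrawn for clinical or symptomatic progression, starts other therapy, stays alive and never has documented objective progression is censored at the switch. Scheduled scans also end there. The clinical failure leads to the censoring, so Kaplan-Meier's assumption of non-informative censoring is doubtful.

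The text also leaves the status of later events unclear. Read literally, only subjects who never progress and remain alive are censored. A switcher who later progresses or dies is then an event, and whether the switch censors a subject depends on what happens afterwards.

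At stake is a secondary, descriptive PFS curve and median in 18 subjects, nine per cohort. No test, power calculation or safety conclusion depends on it.

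**Working it through.** The plan states no expected PFS, event count or power, so there is no figure to reproduce. All event patterns below are assumed, for illustration. The estimator is S(t) = product of (1 − d/n) over event times.

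**Calendar.** The flowchart puts Week 12 at Day 78 and Week 18 at Day 120, so day = 7 × (week − 1) + 1. Week 24 is 7 × 23 + 1 = Day 162 and Week 36 is 7 × 35 + 1 = Day 246. A subject whose last dose and last scan are at Day 120 has contacts to 120 + 100 = Day 220, then one near 220 + 84 = Day 304. Contact can therefore outlast two scheduled scans. Footnote d still schedules both scans, so this subject has departed from the schedule.

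**Unscanned time (n = 9).** Progressions are 2, 1, 1 and 1 at Weeks 12, 18, 24 and 36, and all events fall on scan days. Week 36 PFS is:

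| Pattern | Censored at last contact | Censored at last scan |
|---|---|---|
| All scans on schedule | (5/9)(4/5) = 0.444 | 0.444 |
| One subject misses the Week 36 scan, contacted at Week 37 | (5/9)(4/5) = 0.444 | (5/9)(3/4) = 0.417 |
| One subject has no scan after Week 18, contacted to Day 304 | 0.444 | (6/9)(4/5)(3/4) = 0.400 |

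After Week 24 the curve is at 5/9 = 0.556, or (6/9)(4/5) = 0.533 in the last case. The median is Week 36 throughout.

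**Switchers (n = 9).** Two progressions at Week 12 and one at Week 18; k subjects switch at Day 60 and remain alive without documented progression.

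| k | Week 12, censored | Week 12, event | Week 18, censored | Week 18, event |
|---|---|---|---|---|
| 1 | 6/8 = 0.750 | (8/9)(6/8) = 0.667 | 0.750 × 5/6 = 0.625 | 0.667 × 5/6 = 0.556 |
| 2 | 5/7 = 0.714 | (7/9)(5/7) = 0.556 | 0.714 × 4/5 = 0.571 | 0.556 × 4/5 = 0.444 |

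With k = 1 the median is not reached by Week 18 either way. With k = 2 it is not reached if switchers are censored and is reached at Week 18 if they count as events.

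Pooled (n = 18), with 5, 2 and 1 progressions at Weeks 12, 18 and 24 and two switchers at Week 8, Week 18 PFS is (11/16)(9/11) = 0.563 censored and (16/18)(11/16)(9/11) = 0.500 as events. The median is Week 24 and Week 18 respectively.

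Censoring the Day 60 switchers at Day 1 instead leaves 0.750/0.625 and 0.714/0.571 unchanged, because no event falls in between. Moving the censoring date therefore does not address this mechanism; only an analysis that counts these failures as events shows it.

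**Direction.** In a large-sample simulation (exponential PFS, assumed median 26 weeks, the protocol's scan weeks, data cut at Week 170), the rule as read here was compared with last-scan censoring that counts symptomatic progression as an event. Week 52 PFS was 27.8% under both with neither problem, 31.2% against 27.5% with 10% symptomatic switchers, and 30.2% against 27.7% with 10% unscanned after Week 24 but in contact to the data cut. The rule as read gave higher PFS in every setting where either problem was present.

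**The case against.** The contact reading is not the only one. Section 4.2.1.4 ends by promising effort to follow subjects for progression, while Section 4.2.1.5 promises it for OS. Last follow-up under PFS could therefore mean last follow-up for progression. A reader might infer that the plan definitely counts missed scans as progression-free time. The documents do not establish that; they leave the term undefined.

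The plan also has safeguards:

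- Footnote d schedules scans at Week 24 and every 12 weeks for subjects who have not progressed.
- A final-assessment scan is due about two weeks after the last drug unless one was done in the previous six weeks. A Day 60 switcher last dosed on Day 43 would be due one near Day 57, so the example needs that scan to be missed or negative.
- Section 3.1.16 collects progression dates as well as survival at least every 12 weeks.
- The Section 8.4 note asks for objective progression to be documented even after treatment stops, and Section 7.2.6 asks for a complete final evaluation at withdrawal.
- Section 3.1.8 recommends giving all four combination doses despite apparent clinical progression if performance status is stable, which makes early switching less likely.

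A reader might also infer that every symptomatic progressor is censored. On the literal text, only those who stay alive with no documented progression are. Finally, sampling error is far larger than these shifts: the exact 95% interval for 4/9 is about 14% to 79%.

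All of this limits the size of the problem. None of it sets the censoring date or settles how events after new therapy count.

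**Conclusion.** The point holds at minor-to-moderate weight. The censoring rule is not tied to tumour assessment, and under the contact reading it credits unscanned time. Living switchers without documented progression are probably informatively censored under either reading. Both tend to make PFS look better.

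The effect of unscanned time is nil when scans are on schedule, and 2 to 4 percentage points at Week 36 in the nine-subject examples, with the median unchanged. The switch effect is larger (13 points at Week 18 with two of nine, and a change in whether the median is reached), but it needs an assumed number of early switchers. The pooled example shows that the median can also move with two of 18. The documents give no rate of missed scans or symptomatic switching, so a claim that reported PFS will be materially inflated would go beyond them.

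**What to change.** In Section 4.2.1.4:

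- Censor living non-progressors at the last adequate tumour assessment on or before the start of new therapy, or at Day 1 if there is none after baseline. Count outside imaging whose date is documented.
- State whether progression or death after new therapy counts as an event.
- Keep criteria-based PFS as the main analysis. Add one supportive sensitivity analysis that counts clinical or symptomatic progression leading to withdrawal as an event on the date of withdrawal.

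At the existing Section 3.1.16 contacts, record the date of the latest imaging. That section collects dates of progression and survival but not of negative outside scans. Without this field, outside progressions would count while negative outside scans would not extend follow-up, and last-scan censoring could then bias PFS downwards.

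The cost is a few sentences, one imaging-date field at contacts already planned, and one extra analysis. PFS may look slightly less favourable. The sensitivity analysis rests on open-label investigator judgement, so it should stay supportive.

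### The PFS rule in 4.2.1.4 makes censoring at new treatment depend on what happens after the switch; one rule should cover every switcher

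*Combined protocol and SAP*

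**What the plan says.** Section 4.2.1.4 starts the PFS clock at first dosing and gives the end of the interval as: "to the date of earliest disease progression based on the appropriate response evaluation method, or to the date of death". Nothing there excludes an event that occurs after another anticancer therapy has begun. The censoring sentence is: "Subjects who do not progress and are still alive will be censored on the date of last follow-up or start of new treatment", whichever is earlier. It covers only subjects with neither progression nor death.

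Three other places decide whether post-switch events can reach the analysis:

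- Section 3.1.10 lists "Initiation of alternative anticancer therapy including another investigational agent" as a reason to stop study treatment, not to leave the study. Such subjects go on to Post Study Follow-up.
- Section 3.1.16 says that "clinical outcomes data (dates of progression/relapse and survival) will be collected at least every 12" weeks, for 3 years after the 100-day On Study Follow-up. Section 4.2.1.4 adds: "Every effort will be made to follow subjects for progression after they discontinue the study".
- Section 3.2, footnote d, continues protocol scans "until progression or start of alternate anti-cancer therapy".

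Section 4.2.2 plans the estimate: "Kaplan-Meier methodology will be implemented to estimate the median duration of response, median PFS, and median OS at Weeks 12 and 18". Section 4.2.1.3 defines duration of response "with time origin at the first occurrence of response until the first occurrence of progression or date of death" and states no censoring rule.

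**The concern.** Take two subjects who both start another therapy at month 6 without progression. One progresses at month 20 and enters the analysis as an event at month 20. The other is event-free at month 36 and is censored at month 6. They had the same history at month 6; only the later outcome separates them.

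Kaplan-Meier requires that a subject censored at a given time has the same outlook as those who stay at risk. Here the subjects removed at the switch are exactly those who will do well, while those who will fail keep all their time at risk. This holds even if every date is complete and the choice to switch has nothing to do with prognosis. The resulting PFS is neither censored at new therapy nor analysed regardless of it, and two analysts could draw different curves from the same data. The distortion grows with the share of switchers who stay event-free.

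**Working it through.** **Nothing to reproduce.** The plan gives no PFS figure, event count or switch rate. The inputs from the documents are the event and censoring sentences (4.2.1.4), 9 subjects per cohort and 18 in all (3.1.6), and follow-up of 100 days plus 3 years after the last dose, about 39 months (3.1.16). All other inputs below are assumptions.

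**Three rules compared.** W: as written. A: all progressions and deaths count, with censoring only at last follow-up. C: every event-free switcher is censored at the switch, whatever follows.

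**Direction of W against A.** The Kaplan-Meier curve is the product of (1 − d/Y) over event times, with d events and Y at risk. W and A have the same events at the same times, so d is identical. W removes event-free switchers early, so Y under W is never larger. Each factor, and hence the curve, is equal or lower in any data set. In 32,000 simulated trials of 9 or 18 subjects, W never exceeded A.

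**Example with 9 subjects (invented data).** Events at months 3, 5, 8, 11, 14 and 18; three subjects event-free at month 36. Three subjects switch: one at month 4 (the event at month 11), and two at months 4 and 6 who stay event-free.

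- A, 12 months: 8/9 × 7/8 × 6/7 × 5/6 = 0.556; median 14.
- W, 12 months: 8/9 × 6/7 × 4/5 × 3/4 = 0.457; median 11.
- C, 12 months: 8/9 × 5/6 × 3/4 = 0.556; median 14.

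**Size with durable control.** Assumptions: subjects without durable control have exponential PFS with median 8 months; 30% intend to switch, at months 3-9, unrelated to prognosis; new therapy leaves the hazard unchanged. True 24-month PFS is 0.30 + 0.70 × 2^(−24/8) = 0.388 with 30% durable control, and 0.45 + 0.55 × 0.125 = 0.519 with 45%. Rules A and C recover the true curve up to simulation error.

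| Durable | Actually switch | 24-month PFS, A | 24-month PFS, W | Median, A | Median, W |
|---|---|---|---|---|---|
| 30% | about 22% | 0.388 | 0.337 | 14.5 | 12.9 |
| 45% | about 23% | 0.520 | 0.464 | 28.0 | 20.0 |

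The differences are 5.1 and 5.6 points, and 1.6 and 8.0 months.

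**Size without durable control.** The same 30% intention gives about 18% actual switchers. With 40 months of follow-up, the share censored back is c = 0.30 × 2^(−40/8) = 0.0094. Removing these subjects at time zero is the worst case and gives (0.125 − 0.0094)/(1 − 0.0094) = 0.117 at 24 months, so the error is at most 0.8 points. If follow-up ended at 24 months, c = 0.30 × 0.125 = 0.0375 and the worst case is 0.0875/0.9625 = 0.091, an error of at most 3.4 points (about 3 simulated).

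**Second model.** Exponential PFS with median 12 months, 20% switching, 39 months of follow-up: 24-month PFS 0.249 (A and C) against 0.234 (W); median 11.9 against 11.8 months.

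**Weeks 12 and 18.** In the durable-control model, where switching starts at month 3, W differs from the true curve by at most 0.001.

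**Direction of W against C.** If new therapy halves the hazard, W can lie above C. With no durable control and 18% switching, 24-month PFS is 0.138 (W) against 0.125 (C). In the exponential model with median 12 months and 40% switching, W is 0.508 against 0.499 at 12 months, but 0.079 against 0.126 at 36 months.

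**The case against.** The strongest reply is that the sponsor meant follow-up for PFS to end at the switch. Progression counts only by the applicable response method, protocol scans stop when other therapy starts, and later progression dates may come from outside records or contact with the subject or physician. Post-switch progression by protocol criteria is therefore not assured. This stands as evidence of intent, but it does not repair the rule. Footnote d is a scan schedule, not a censoring rule; post-switch deaths would still count; and 3.1.16 and 4.2.1.4 both ask for progression to be followed.

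A reader might infer that the written rule biases PFS downward whatever the comparison. The documents do not support that. The direction is certain only against the all-events definition; against censoring every switcher it can reverse, as shown above.

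The size is also open to challenge. The 8-month shift in the median arises because 45% durable control holds the curve close to 0.5, where a small vertical change moves the median far. About 22% switching before progression would mean 4 of 18 subjects. At 24-month PFS of 0.39 the binomial standard error is √(0.39 × 0.61/9) = 0.16 for 9 subjects and 0.11 for 18, two to three times the 5-6 point error. All of this stands, and it limits the consequence rather than the defect.

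Finally, the missing censoring rule for duration of response is a gap of its own. It is not evidence of the PFS problem.

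**Conclusion.** The concern holds in this form: as worded, 4.2.1.4 lets the later outcome decide whether a switcher is censored, and no other section corrects it. Relative to the protocol's own event definition, the PFS curve can only be equal or lower.

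The size rests on assumed switch rates, durable control and follow-up. It is about 5-6 points at 24 months and 1.6-8 months on the median with 22-23% switching and 30-45% durable control. It is under 1 point with no durable control, 18% switching and about 40 months of follow-up, and near zero at Weeks 12 and 18. The 24-month figures illustrate size only; the plan names medians and Weeks 12 and 18.

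It would be wrong to conclude that the trial's decisions are at risk. PFS is secondary and descriptive, and neither a test nor the step to Cohort B uses it. This is a low-consequence correction worth making because it is cheap and because two affected subjects in a cohort of 9 can move the median.

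**What to change.** Reword 4.2.1.4 so that one rule covers every switcher, for example: *Subjects who start new anticancer treatment before documented progression or death are censored at the date of that start, whatever happens afterwards.* Report the other consistent rule, with all progressions and deaths counted regardless of new treatment, as a sensitivity analysis. Either could be primary; what matters is that the later outcome plays no part. The sensitivity analysis is useful because switching may itself be related to prognosis, in which case censoring all switchers has a bias of its own.

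State the same rule in 4.2.1.3, so that a responder who switches is handled alike in PFS and duration of response.

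The cost is one sentence in each section, one extra Kaplan-Meier run and slightly fewer PFS events. The only date needed is the start of new treatment, which the present rule already requires.
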